8.1.3 Study drug interruption or discontinuation

The investigator must temporarily interrupt or permanently discontinue the study drug if continued administration of the study drug is believed to be contrary to the best interests of the patient. The interruption or premature discontinuation of study drug might be triggered by an AE, a diagnostic or therapeutic procedure, an abnormal assessment (e.g., laboratory abnormalities), or for administrative reasons, in particular withdrawal of the patient's consent.

Hypertriglyceridemia: The study drug will be interrupted for 24 hours at triglyceride levels > 400 mg/dl or down titrated at triglyceride levels of 251-400 mg/dl. Control measurements of triglyceride levels will be performed in the next 24-72 hours to control for successful normalization of triglyceride levels under parenteral nutrition.

The reason for study drug interruption or premature permanent discontinuation must be documented in the CRF.

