8.1.10 Concomitant medication

The well-being of the patient has the first priority, and modifications of concomitant treatment during the trial are allowed as necessary. They should be documented in the patient's records.

In case of of cholestasis (i.e. conjugated bilirubin two times > 1.5 mg/dl),

Ursodeoxycolic acid at 20-30 mg/kg/day is the treatment of choice.

Omegaven® is allowed as add on at 1g/kg/d, if conj. bilirubin > 6 mg/dl,

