11.1 Analysis sets

Two different analysis sets are defined:

(Modified) Intention to treat set

This analysis set includes all subjects where the outcome can be calculated (more than two blood samples taken), even though the subject was not observed the full 18 weeks.

Per-protocol set

This analysis set comprises all subjects who were observed the full 18 weeks, received the study drug as planned and did not violate the protocol in a way that might affect the evaluation of the effect of the study drug on the primary objective, i.e., without major protocol violations.

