11.4 Statistical analysis plan

A **statistical analysis plan (SAP)** will provide full details of the analyses, the data displays and the algorithms to be used for data derivations. The SAP furthermore will include definitions of major and minor protocol deviations and the link of deviations to the analysis set, which also will be covered in the final study report.

Procedures of reporting any deviations from the original statistical plan (any deviations from the original statistical plan should be described and justified in the protocol and/or in the final report, as appropriate.

The SAP should preferably be a separate document. In the protocol this document should be referenced. Alternatively the SAP could be fully included in the study protocol.

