11.5 Missing, unused and spurious data

If less than two blood samples of a patient were taken, the outcome cannot be calculated and therefore, this patient will be excluded from the analysis. The analysis will be carried out per protocol.

If the outcome of a patient can be calculated (more than two blood samples taken) but the patient was withdrawn from the study before week 18, analysis will be carried out 1) by intention to treat analysis, with the duration of treatment as additional covariable and 2) per protocol.

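### The per-protocol set has no cut-off at PNAC, so an infant whose study lipid is interrupted or stopped because of PNAC can be excluded for having had the event

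*Combined protocol and SAP*

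**What the plan says.** Section 11.1 defines two sets.

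- **Modified intention to treat:** "This analysis set includes all subjects where the outcome can be calculated (more than two blood samples taken"), including infants not followed for the full 18 weeks.
- **Per protocol:** infants observed for the full 18 weeks who "received the study drug as planned and did not violate the protocol in a way that might affect the evaluation of the effect", that is, without a major violation bearing on the primary objective.

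Section 11.5 uses both for infants withdrawn early: "analysis will be carried out 1) by intention to treat analysis, with the duration of treatment as additional covariable and 2) per protocol". No section names either set as primary. Section 11.4 leaves part of the definition open: "The SAP furthermore will include definitions of major and minor protocol deviations and the link of deviations to the analysis set".

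The endpoint (synopsis and 6.1) is conjugated bilirubin above 1.5 mg/dl on two consecutive occasions. On treatment changes, the protocol says the following.

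- **8.1.3:** interruption or permanent discontinuation "might be triggered by an AE, a diagnostic or therapeutic procedure, an abnormal assessment (e.g., laboratory abnormalities") or by administrative reasons.
- **8.1.4:** a permanent stop for a reason other than an adverse event leads to withdrawal from the study. A stop for an adverse event leads to a premature end-of-study visit.
- **9.1.2:** endpoint occurrences are not adverse events unless defined otherwise.
- **7.1.5:** withdrawal is tied to an 80% drug-provision threshold (the wording is garbled), with no reference to the endpoint date.
- **8.1.10:** ursodeoxycholic acid is named for cholestasis, and Omegaven "is allowed as add on at 1g/kg/d, if conj. bilirubin > 6 mg/dl".

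**The concern.** PNAC status is settled at the second qualifying bilirubin value. Nothing done to the lipid afterwards can change whether that infant is a case. Yet 11.1 tests adherence and observation over the whole course, so later events can decide whether the case is counted.

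Infants without PNAC may leave the set for other reasons, but not for this one. The exclusion therefore depends on the outcome, which a per-protocol set should avoid. Section 11.5 prescribes the per-protocol result and no hierarchy is stated, so a reader could give it the same weight as the intention-to-treat result. Removing cases lowers the observed incidence in both arms and costs power. If the arms lose cases at different rates, the treatment comparison itself is biased.

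**Working it through.** **Route through the text.** Take an infant who meets PNAC and whose lipid is then permanently stopped under 8.1.3, where the triggers include "an abnormal assessment (e.g., laboratory abnormalities").

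1. If PNAC is not an adverse event (9.1.2), 8.1.4 has the infant withdrawn from the study.
2. If the bilirubin finding is handled as an adverse event (9.1.2 also lists laboratory findings that lead to discontinuation), 8.1.4 gives a premature end-of-study visit.
3. Either way the infant can fail both the as-planned and the 18-week conditions of 11.1.
4. A temporary interruption leaves the infant under observation but can still breach the as-planned condition, or the 7.1.5 threshold if it is long enough.
5. Whether the permitted Omegaven add-on departs from the plan is not stated. The synopsis also requires raised liver enzymes and gives a dose range, while 8.1.10 does neither. The two passages must be reconciled before any deviation list can refer to them.

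**The plan's own figure.** Inputs from 11.2 and the synopsis: 25% vs 10%, two-sided 0.05, power 80%. The mean rate is 0.175.

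n = [1.96·√(2·0.175·0.825) + 0.8416·√(0.25·0.75 + 0.10·0.90)]² / 0.15² = (1.0532 + 0.4434)² / 0.0225 = 99.5, so 100 per group. The plan's figure reproduces. Power at 100 per group is 80.2% by the normal approximation and 81.6% by exact enumeration of the Pearson χ² test.

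**Effect of removal.** Let f be the share of PNAC cases that leaves the per-protocol set. The documents give no value, so every f below is an assumption. Starting from n = 100 per group:

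- observed rate p′ = p(1 − f)/(1 − pf)
- remaining size n′ = n(1 − pf)
- odds p′/(1 − p′) = p(1 − f)/(1 − p), so the odds ratio (Intralipid vs SMOFLipid) is 3.0·(1 − f_I)/(1 − f_S)

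Example, f = 0.5 in both arms: 0.125/0.875 = 14.3% and 0.05/0.95 = 5.3%.

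Exact power uses group sizes rounded to whole infants.

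| f Intralipid / SMOFLipid | Rates | Difference (points) | Odds ratio | Exact power |
|---|---|---|---|---|
| 0 / 0 | 25.0% vs 10.0% | 15.0 | 3.0 | 82% |
| 10% / 10% | 23.1% vs 9.1% | 14.0 | 3.0 | 78% |
| 20% / 20% | 21.1% vs 8.2% | 12.9 | 3.0 | 73% |
| 50% / 50% | 14.3% vs 5.3% | 9.0 | 3.0 | 54% |
| 40% / 10% | 16.7% vs 9.1% | 7.6 | 2.0 | 34% |
| 50% / 25% | 14.3% vs 7.7% | 6.6 | 2.0 | 30% |
| 25% / 50% | 20.0% vs 5.3% | 14.7 | 4.5 | 89% |

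With equal removal the absolute difference and the power fall, but the odds ratio stays at 3.0 and the risk ratio rises slightly (2.50 to 2.71 at 50%). With unequal removal the odds ratio moves in either direction.

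**The case against.** **No rule stops the lipid at PNAC.** A reader might infer that infants with PNAC are taken off study lipid, or switched to another, and so are removed as a matter of course. The documents do not support that. The synopsis and 8.1.10 name ursodeoxycholic acid. Omegaven is allowed only above 6 mg/dl, and 8.1.10 calls it an add-on, not a replacement. Section 8.1.3 is a general best-interest clause, and the only laboratory abnormality for which it sets an action is hypertriglyceridaemia. This stands: infants can be removed, not are removed.

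**The SAP may close the gap.** Section 11.4 defers deviation definitions, and the closing words of the per-protocol definition can be read as reducing all its conditions to major violations affecting the primary objective. On that reading a change after PNAC would not count. This is fair, but as written the as-planned and 18-week conditions stand beside the violation clause, and nothing tells the SAP author to stop the clock at PNAC.

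**Overlap with the 18-week condition.** A permanent stop followed by withdrawal may already fail the observation requirement. This is correct, so a fix limited to adherence would be incomplete.

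**A false positive is not shown.** A reader might go further and infer that the trial could produce a spurious effect. With 17.5% in both arms and 50% vs 20% of cases removed, the rates become 9.6% vs 14.5% and the rejection rate is 0.175, against 0.051 without removal. That needs equal incidence together with very unequal stopping, while prescribing doctors are blinded (8.3). It shows what is possible and estimates nothing.

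**The remedy has its own asymmetry.** Cases would be judged over a shorter window than non-cases. If 10% of all infants deviated late for unrelated reasons (an assumption), cases would stay and non-cases would leave: 25/(25 + 75·0.9) = 27.0% and 10/(10 + 90·0.9) = 11.0%. This is a small, real cost and should be disclosed.

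**Conclusion.** The concern holds in a limited form. Section 11.1 sets no endpoint cut-off for adherence or observation, and 8.1.3, 8.1.4, 9.1.2 and 7.1.5 together supply a route by which an infant leaves the per-protocol set because of PNAC. It is a defect in a prescribed analysis and should be corrected.

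Its size is unknown. Equal removal of 10% to 50% of cases would cost about 1 to 6 points of the 15-point difference and bring exact power from about 82% down to between 78% and 54%. These figures start from 100 evaluable infants per group, ignore other per-protocol exclusions, and rest on assumed removal shares.

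It would be wrong to infer that the trial's main comparison is compromised. The modified intention-to-treat set keeps infants with more than two samples even if they are withdrawn, so this mechanism does not reach it. The one unclear case is an infant with exactly two samples, which suffices for PNAC but not for the set as worded. What leaves the matter open is that no section makes modified intention to treat the primary analysis.

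**What to change.** Amend 11.1 to state that:

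- for infants who meet PNAC, per-protocol adherence, deviations and the observation requirement are assessed only up to the second qualifying bilirubin value;
- for infants who do not, they are assessed to the end of the planned treatment and observation period;
- changes to study drug, or to concomitant lipid that the protocol permits, made after PNAC do not remove an infant from the set;
- modified intention to treat is the primary analysis and per protocol is supportive.

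Apply the same cut-off to the deviation list promised in 11.4. Because cases then have less time in which to deviate, report per-protocol exclusions by arm and PNAC status.

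The cost is a few sentences in 11.1 and the SAP, plus one table. No new data are needed: procedures are dated (8.5.1), reasons for interruption go in the CRF (8.1.3), and administration is recorded (8.1.8, 8.1.9). Clinical management does not change.

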11.2 Sample size considerations

Data investigating the incidence of PNAC in our unit showed an incidence of 25 % from 2007-9 (unpublished data). We considered a difference of 15% between the groups (incidence of PNAC: 25% for Intralipid and 10% for SMOFLipid, respectively) as a clinically relevant effect. A sample size estimation based on a χ^2 -test indicated that 200 infants (100/group) are required to detect a difference of 15% between the groups with a power of 80% and a significance level of 0.05. The estimated drop out rate is 22%. Therefore, a sample size of 122 patients per group is planned. For sample size estimation, data were assumed to be independent.

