2. PROTOCOL SYNOPSIS

TITLE	Preventing Cholestasis in Premature Infants Using SMOFLipid®					
OBJECTIVES	
Primary Objective
 
 To compare a mixed parenteral lipid emulsion containing fish oil (SMOFLipid®) with a soybean oil based lipid emulsion (Intralipid®) for its effect on the occurrence of parenteral nutrition associated cholestasis in extremely low birth weight infants 
Secondary Objectives
 
 To assess the impact of SMOFLipid® on the long term neurocognitive development of extreme low birth weight infants at 12 and 24 months of corrected age 					
DESIGN / PHASE	Prospective, randomized, double-blind, phase IV study.					
STUDY PLANNED DURATION	First patient First visit	1st month	Last patient First visit	36 month s	Last patient Last visit	62 months
CENTER(S) / COUNTRY(IES)	Single center, Austria (Medical University Vienna, Austria; Department of Neonatology, Pediatric Intensive Care and Neuropediatrics, University Children's Hospital,)					
PATIENTS / GROUPS	
200 patients in 2 groups 100 patients per group Block randomization ratio 1:1, stratification by sex and weight (in two groups: < 750 gram vs. ≥750 gram).
 
In case of twins, randomization will be applied to the firstborn; the twin will be assigned to the other treatment group. Triplets or higher will be excluded.
					
INCLUSION CRITERIA	
 Infants born with a birth weight ≤ 1000 Gram (= extreme low birth weight infants) Admission to the neonatal ward in the first 24 hours of life Informed consent obtained and randomized on study drug the first 5 days of life 					
EXCLUSION CRITERIA	
 Triplets or higher Conjugated bilirubin > 1.5 mg/dl before inclusion to the study Conditions associated with cholestasis independent of parenteral nutrition: 
 Inborn errors of metabolism Viral Infections (cytomegaly virus, HIV, Hepatitis B, C) Immune mediated hemolytic disease (e.g. Rhesus incompatibility) Cystic fibrosis Primary cholestatic diseases of the liver For Neurodevelopmental outcome in follow up phase: Congenital neurological malformations and chromosomal aberrations 					

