STATISTICAL METHODOLOGY	
Primary Endpoint PNAC (definition see efficacy endpoint)
 
Null and alternative hypotheses: H₀ : The percentage of PNAC in group 1 (investigational drug) equals group 2 (comparative drug) H₁: The percentage of PNAC in group 1 (investigational drug) does not equal group 2 (comparative drug)
 
Sample size calculation A sample size estimation using a χ^2-test indicated that 200 infants (100/group) are required to detect a 15% difference (10% in group 1 vs. 25% in group 2) with a power of 80% and a two-sided significance level of 0.05. The estimated drop out rate is 22%. Therefore, a sample size of 122 patients per group is planned. For sample size estimation, data were assumed to be independent.
 
Statistical methodology Main analysis set(s) A χ^2-test will be used for analysis of the primary outcome PNAC. Additionally, the effect of treatment and other relevant influence factors (i. e. duration of parenteral nutrition, birth weight, necrotizing enterocolitis) on the primary endpoint will be analyzed using a logistic regression model with

	
stepwise selection. In case of twins, the analysis will be carried out 1) as mentioned above, but only including the firstborn and 2) by calculating a generalized linear model with mother as random factor.
 
Other endpoints
 
Bailey Scales of Infant Development III at 12 and 24 months: Differences in the scores of psychomotor development and neurocognitive development, respectively, between the groups will be analyzed by repeated measures ANOVAs, also accounting for confounder factors (e.g. birth weight, ...). In case of twins, the analysis will be carried out 1) as mention above, but only including the firstborn and 2) by calculating a mixed model with mother and child as random factor. In case of too many drop outs, descriptive statistics will be carried out.
 
For Gross Motor function measurements at 12 and 24 months, descriptive statistics will be conducted.

--	--

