7. STUDY DESIGN

7.1 Study population

7.1.1 Subject population

Population: Extreme low birth weight (ELBW) infants

Recruitment: About 90 ELBW infants are admitted to our unit each year in the first 24 hours of life.

We expect to recruit 90 % (81 patients/a year) to the study.

Drop Outs: Based on a mortality of 22% in 2010 ([name], unpublished data) and a conservative calculation, we expect 18/81 patients to drop out, leaving 63 patients a year for analysis of the primary outcome. We do not expect any other reasons for drop out.

Losses to follow up: 63 patients are expected to be discharged from hospital each year. Based on a follow up rate of 60% after discharge in 2009 ([name], unpublished data), we expect about 38/63 patients to be available for analysis of the secondary outcome each year. In the end we expect to lose 80/200 patients to follow up.

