7.1.5 Withdrawal and replacement of subjects

Criteria for withdrawal

Premature discontinuation from the study is to be understood when the subject did not undergo End of Study (EOS) examination and / or all pivotal assessments during the study.

Subjects must be withdrawn under the following circumstances:

- at their parent's request at any time
- if the investigator feels it would not be in the best interest of the subject to continue
- if the subject violates conditions laid out in the consent form / information sheet or disregards instructions by the study personal
- if the subject is transferred to another hospital before parenteral nutrition is discontinued
- if the study drug was not provided < 80% of time as planned per protocol
- If an exclusion criterion is met, after inclusion to the study (except neurological malformation and chromosomal aberration which only leads to withdrawal from follow up analysis except screening for adverse events)
- death before day of life 28

In all cases, the reason why subjects are withdrawn must be recorded in detail in the CRF and in the subject's medical records. Should the study be discontinued prematurely, all study materials (complete, partially completed and empty CRFs) will be retained.

Follow-up of patients withdrawn from the study

In case of premature discontinuation after study drug intake, the investigations scheduled for the EOS visit will be performed 7 +/-4 days after study drug discontinuation. The subjects will be advised that participation in these investigations is voluntary. Furthermore, they may request that from the time point of withdrawal no more data will be recorded and that all biological samples collected in the course of the study will be destroyed.

Replacement policy

Patients withdrawn from the study < 28 days (outcome cannot be calculated) will be replaced and the next free subject number will be allocated. Drops outs will be included in the sample size. If patients are withdrawn from the study and the outcome can be calculated, (more than two blood samples taken), they will be considered in the intention to treat analysis (see chapter 10)

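### Minor arithmetic error: the 22% drop-out allowance was applied as 100 × 1.22 = 122 per group instead of 100 / 0.78 = 129, so 122 leaves about 95 evaluable per group if the full loss occurs and is not additionally replaced

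*Combined protocol and SAP*

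**What the plan says.** Section 11.2 assumes "incidence of PNAC: 25% for Intralipid and 10% for SMOFLipid, respectively" and concludes that "200 infants (100/group) are required to detect a difference of 15% between the groups"; it sets the power at 80% and the level at 0.05. The synopsis gives the same calculation and adds that the level is two-sided: "with a power of 80% and a two-sided significance level of 0.05". Both places then make the allowance for losses: "The estimated drop out rate is 22%. Therefore, a sample size of 122 patients per group is planned".

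Section 7.1.1 shows where the 22% comes from. It is the unit's 2010 mortality, applied to the expected yearly recruitment of 81: "we expect 18/81 patients to drop out, leaving 63 patients a year for analysis of the primary outcome".

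Two other places bear on the enrolled number. The Patients / Groups row of the synopsis says "200 patients in 2 groups 100 patients per group", without saying whether this means enrolled or evaluable. Section 7.1.5 replaces infants withdrawn before day 28 whose outcome cannot be calculated, and then adds: "Drops outs will be included in the sample size".

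**The concern.** A drop-out rate expressed as a share of those enrolled is allowed for by dividing the evaluable number by one minus the rate. Multiplying by one plus the rate is right only if the rate is a share of those who remain. Section 11.2 multiplies, while section 7.1.1 defines the rate on recruited infants. The enrolment figure therefore does not follow from the plan's own inputs.

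What is at stake is the accuracy of two reported figures, the planned enrolment and the power. It also matters that the site can tell which number ends recruitment: the synopsis row shows 200, the statistical text implies 244, and section 7.1.5 does not say how replacements count towards either.

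**Working it through.** **Inputs.** Event rates 25% and 10% (11.2); two-sided 0.05 (synopsis); power 80% (both); uncorrected χ²-test (11.2 and 11.6.1 name the test and mention no continuity correction); 1:1 allocation (8.2); loss 22% of recruited infants (7.1.1: 18/81 = 22.2%).

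**1. The base of 100 reproduces.** With p̄ = 0.175 and d = 0.15, the pooled-variance formula is

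n = [1.960 × √(2 p̄(1 − p̄)) + 0.842 × √(p₁(1 − p₁) + p₂(1 − p₂))]² / d²

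= [1.960 × √0.28875 + 0.842 × √0.2775]² / 0.0225 = 99.5, so 100 per group.

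The base is correct. The problem lies only in the next step.

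**2. The allowance for losses.**

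- As planned: 100 × 1.22 = 122 per group (244).
- Matching the definition in 7.1.1: 100 / 0.78 = 128.2, so 129 per group (258).
- Difference: 7 per group, 14 in total.

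**3. What 122 leaves if 22% are lost.** 122 × 0.78 = 95.2 per group, about 190 in total. That is about 5 per group, or 10 in total, below the stated requirement. For comparison, 129 × 0.78 = 100.6.

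**4. Power for 25% vs 10%.**

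| Evaluable per group | Normal approximation | Exact enumeration, uncorrected χ² |
|---|---|---|
| 95 | 78.1% | 79.2% |
| 100 | 80.2% | 81.6% |

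The approximation is Φ[(0.15√n − 1.960 × √0.28875) / √0.2775].

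**5. The loss at which 122 is enough.** 1 − 100/122 = 18.0%. So 122 per group delivers 100 evaluable if no more than 18% are lost. That would be so if about 4 of the 22 percentage points turned out to be evaluable after all.

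**6. Accrual.** 81 a year over the 36 months between first and last patient's first visit gives 81 × 3 = 243, in line with 244 enrolled. The evaluable yield is 63 × 3 = 189. This is the same 22% applied to the same recruits, so it agrees with step 3 but does not confirm it independently.

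**The case against.** The strongest reply is that the loss of 22% is itself a cautious figure. Section 7.1.1 uses overall mortality and calls the calculation conservative. Sections 7.1.5 and 8.5.4 treat only death before day 28 as a drop-out, and sections 7.1.5 and 11.1 keep any infant with more than two blood samples in the modified intention to treat set. Deaths after day 28 with enough samples would therefore count as evaluable, and step 5 shows that few are needed to bring the loss down to 18%. This stands as a possibility. The documents do not give the timing of deaths, and section 7.1.1 counts all 18 of 81 as lost to the primary outcome, so about 95 remains the plan's own implied figure.

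The second reply is replacement. If infants replaced under section 7.1.5 come on top of the 122, the shortfall does not arise. This also stands as a possibility. The sentence that includes drop-outs in the sample size points the other way, towards replacement within the 122, but does not settle it.

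A third reply is that another formula might explain 122. An unpooled variance gives a base of 97, and 97 / 0.78 rounds up to 125. That is closer but still not 122, and the plan states a base of 100.

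A reader might go further and infer that early deaths are handled twice, once by the allowance and once by replacement. That follows only if replacements come on top of the 122. In that case the shortfall disappears, so the two criticisms cannot both be pressed. Nor does any section set 244 evaluable infants as a target, so a much longer recruitment period cannot be derived from the replacement rule.

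**Conclusion.** The step from 100 to 122 is wrong as written: on the plan's own definition of the 22%, the matching figure is 129 per group. If 22% of enrolled infants are lost and not replaced on top of the 122, about 95 per group are evaluable and power is about 78% (normal approximation) or 79% (exact), against the stated 80%.

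This is a minor correction. A reader might infer that the trial is materially underpowered, but the gap is only about 1 to 2 percentage points and depends on both of those conditions. The 95 also refers to all infants with a calculable outcome. The firstborn-only analysis in section 11.6.1 would use fewer, by a number the documents do not give.

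Nor do the documents show three competing enrolment targets. The synopsis itself gives both 200 required and 122 per group planned, and section 7.1.1 uses 200 as the base for its expected 80 losses to follow-up after discharge. The 200 in the Patients / Groups row is therefore most plausibly the evaluable number without a label. The unlabelled figure and the unclear replacement rule still need tidying.

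**What to change.** In section 11.2 and the synopsis, keep 122 per group (244) and add a sentence such as: *assuming that 22% of enrolled infants are not evaluable and are not additionally replaced, about 95 per group are evaluable, giving a power of about 78% for 25% vs 10%*. If the 80% claim is to be kept under those assumptions, the matching figure is 129 per group (258).

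Label the 200 in the synopsis Patients / Groups row and in section 7.1.1 as evaluable infants, and show the enrolled number (244) beside it. State in section 7.1.5 whether replacements fall within the 122 per group or come on top of it.

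Keeping 122 costs protocol wording and a slightly lower stated power. Moving to 129 costs 14 more infants, about two months at the expected 81 recruits a year (14 / 81 × 12 = 2.1), and the enrolled numbers above would then read 258 and 129.
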